The HIRREM process is individualized for each recipient, such that the specific protocols chosen, the session length, and the total number of sessions are variable. Technologists time sessions and chose protocols to facilitate an overall trend toward greater hemispheric symmetry and more optimal proportionation in frequency ranges, between and within cortical regions, based upon data from the initial assessment and the ensuing sessions (Gerdes et al., 2013). Each participant in the HCC group will receive at least 10 sessions. The final number of HIRREM sessions, which may be extended to as many as 16, will depend on continuous review of brain patterns relative to progress towards improved balance and quieting of electrical amplitudes, as well as progress and stability of self-reported status regarding symptoms such as sleep and stress.

Ambient nature sounds (NCC) were chosen as an active control because this approach may also facilitate recovery from stress-related sympathetic hyperarousal (Alvarsson, Wiens, & Nilsson, 2010). Exposure to nature sounds has been shown to facilitate reduced sympathetic activation in response to psychological stress (Annerstedt et al., 2013), which is relevant for those with hypertension, and also provides a credible control regarding the effects of expectation associated with a technological intervention, while also matching exposure to location, environment, exposure time, and staff contact for each study group.

Participants assigned to the NCC group will receive sessions in the same rooms, but will select from a variety of ambient sounds. Sessions will consist of 60-90 minutes of listening time, while in a zero gravity chair, and are intended to mirror the time, environment, eye state, and staff interaction

experienced by the HCC group. Technologists will interact with the participant during the sessions, as they would with HIRREM sessions, requesting that some portions are with eyes open, and others with eyes closed. As with the real HIRREM sessions, if eyes closed segments the participant may recline and drift to sleep, while with eyes open, they may just relax, or engage in activities such as reading, or a word search. In order to achieve comparability with the HCC group, including potential effects of exposure time to the environment and study personnel, those randomized to the NCC group will also receive between 8-16 sessions. The number of sessions for the NCC group will be randomly assigned via a second randomization, following their assignment to the NCC group.

Safety:

Evidence to date indicates that the HIRREM intervention is potentially high benefit and low risk. Based on experience reported by Brain State Technologies, garnered from provision of case management support, feedback from their clients, and feedback from the HIRREM provider community, as well as from our IRB-approved studies at WFSM (now over 450 participants to receive HIRREM), we are not aware of any serious adverse events resulting from HIRREM sessions. A few participants undergoing HIRREM have reported experiencing emotions, both positive and negative, primarily during initial sessions. These have been similar to the range of emotions one might experience in the course of everyday life events, and have been transient, resolving over a few minutes or hours, to several days. In the course of providing HCC to over 450 individuals participating in one of five IRB-approved research studies at WFSM, such mild symptoms have been estimated to occur in less than 5 percent of participants, and none have experienced prolonged or intense changes in emotional state, or required additional treatment. All HIRREM sessions are administered by Technologists who have been certified in the procedure, including guidelines for addressing emotional releases that may occur. In the event that emotional releases are prolonged or intense, individuals would be advised to see a mental health professional for additional evaluation or treatment, or if acute, will be referred to the Emergency Department. There have been no instances in the > 440 subjects participating to-date of prolonged or intense changes in emotional state. There are no anticipated risks associated with listening to ambient nature sounds.

Other Data Collection, Measures, and Process:

A series of measures will be collected at the enrollment visit (V1), as well as at three post-intervention visits for all participants.

Demographics:

Demographic information will include embedded elements to allow calculation of the Charlson Comorbidity Index Score (Charlson et al., 2008).

Autonomic cardiovascular Regulation [Blood Pressure (BP), Heart Rate (HR), Heart Rate Variability (HRV), Baroreflex Sensitivity (BRS), and Blood Pressure Variability (BPV)]:

Continuous BP and HR are acquired from noninvasive finger arterial pressure measurements and ECG for a minimum of 10 minutes in subjects lying down quietly, supine. Systolic BP and beat to beat, RR, intervals (RRI) files generated via the data acquisition system (BIOPAC acquisition system and software, Santa Barbara, CA) at 1000 Hz are analyzed using Nevrokard SA-BRS software (by Nevrokard Kiauta, d.o.o., Izola, Slovenia) for measures of BRS, HRV and BPV as follows: Frequency Method. Power spectral densities of SBP and RRI oscillations are computed by 512 points Fast Fourier Transform (FFT) and integrated over specified frequency ranges (LF: 0.04-0.15 Hz; HF: 0.15-0.4 Hz). A Hanning window is applied and the squared-coherence modulus is computed if coherence is >0.5 as reported. The square-root of the ratio of RRI's and SBP powers is computed to calculate LF, HF alpha indices, which reflect BRS (16). Power of RRI spectra in LF, HF range (LFRR and HFRR) are calculated in normalized units and the ratio of LFRR/HFRR is used as a measure of sympathovagal balance. Power of SBP spectra calculated as LFSAP is used as a measure of BPV. Sequence Method. BRS calculated by this method is based on quantification of sequences of at least three beats (n) in which SBP consecutively increases (UP sequence) or decreases (DOWN sequence), which are accompanied by changes in the same direction of the RRI of subsequent beats (n+1). The software scans the RRI and SBP records, identifies sequences, and calculates linear correlation between RRI and SBP for each sequence. If the correlation coefficient exceeds a pre-set critical value (0.85), the regression coefficient (slope) is calculated and accepted. The mean of all individual regression coefficients (slopes), a measure of sequence BRS, is then calculated for Sequence UP, DOWN and TOTAL. Time-Domain Analysis. Three time-domain parameters are used for hemodynamic variability. HRV is determined by computing the standard deviation of normal to normal intervals (SDNN), and the root mean square of successive beat-to-beat differences in R-R interval duration (rMSSD). BPV is the standard deviation of the mean arterial pressure (SDMAP).

HRV and BRS Data Processing and Interpretation:

Heart rate is measured as beat-to-beat intervals (RRI) recorded by pulse-wave recording, and will be analyzed using custom software developed by Matlab. Data can be loaded and viewed, and a subset of the data can be selected to avoid artifacts during device placement or removal. Outlier identification is performed by determining all IBIs which demonstrate a 30% difference from the mean of the previous four samples. Such outliers are removed from the data set. HRV statistics that are generated include mean, variance, SDNN, rMSSD, VLF, LF, HF, TP, LF/HF, sample asymmetry, sample entropy, and coherence ("Heart rate variability: standards of measurement, physiological interpretation and clinical use. Task Force of the European Society of Cardiology and the North American Society of Pacing and Electrophysiology," 1996). All of the algorithms for computation of these parameters are derived from information or source code from the Physionet archive. Data are saved to Excel spreadsheets for further statistical analysis by study team members.

Blood Pressure (BP):

For evaluation of blood pressure (BP) values that will be used to qualify for participation in the study, and for analysis of the primary outcomes, BP measurements will be obtained using an automated oscillometric blood pressure device. BP will be obtained in the left arm, with the participant sitting

comfortably, and the left arm resting on a desk/table. Three samples will be obtained and the last two averaged to get the value that will be used as the reading for that visit (Kaplan NM, 2010).

Insomnia:

The severity of insomnia symptoms is measured using three self-report symptom inventories with each data collection visit (Appendix A). This includes the Insomnia Severity Index (ISI), the Pittsburgh Sleep Quality Index (PSQI), and the Epworth Sleepiness Score (ESS). The ISI is a 7 question measure, with responses from 0-4 for each question, yielding scores ranging from 0-28 (Bastien, Vallieres, & Morin, 2001; Morin, Belleville, Belanger, & Ivers, 2011). The PSQI is a 19 item inventory that assesses sleep quality over a 1-month time interval (Buysse, Reynolds, Monk, Berman, & Kupfer, 1989). Items are weighted on a 0-3 interval scale. A global PSQI score is calculated by totaling the seven component scores, providing an overall score ranging from 0 to 21, where lower scores denote a healthier sleep quality. The ESS measures a person's general level of daytime sleepiness, or their average sleep propensity in daily life. The simple questionnaire is based on retrospective reports of the likelihood of dozing off or falling asleep in a variety of different situations. Rated on a 4-point scale (0-3), it evaluates their usual chances of dozing off or falling asleep while engaged in eight different activities. The ESS score (the sum of 8 item scores, 0-3) can range from 0 to 24 (Johns, 1991).

Behavioral and Psycho-physiological function:

Depression:

The Center for Epidemiologic Studies Depression Scale (CES-D) is a depression scale which will help to assess this co-morbidity. CES-D is a 20-item survey assessing affective depressive symptomatology to screen for risk of depression (Radloff, 1977). Scores range from 0-60, with a score of 16 commonly used as a clinically relevant cut-off (SmarrK.L., 2003).

Anxiety:

The Generalized Anxiety Disorder-7 (GAD-7) is a seven item screening tool for anxiety that is widely used in primary care. GAD-7 is a brief, reliable and valid measure of assessing generalized anxiety disorder (Spitzer, Kroenke, Williams, & Lowe, 2006).

Traumatic Stress:

The PTSD Checklist for civilians (PCL-C), measures the American Psychiatric Association's Diagnostic and statistical manual of mental disorders (DSM-IV) Criteria B, C, & D of PTSD symptoms based on traumatic life experience related to military service. Seventeen items are rated on a Likert scale with a composite score range of 17 to 85. A score of 44 or higher correlates with probability of civilian-related PTSD (Blanchard, Jones-Alexander, Buckley, & Forneris, 1996; FW, BT, DS, JA, & TM).

Stress:

The Perceived Stress Scale (PSS) is a ten-item psychological instrument for measuring the perception of stress. It is a measure of the degree to which situations in one's life are appraised as stressful. Items were designed to tap how unpredictable, uncontrollable, and overloaded respondents find their lives. The scale, with answers rated from 0-4, also includes a number of direct queries about current levels of experienced stress (Cohen, Kamarck, & Mermelstein, 1983).

Quality of Life:

The Quality of Life Scale (QOLS) is a 16-item scale that was modified from a 15-item scale used in chronic disease patients. Topics include different components of daily life such as relationships, community engagement, personal fulfillment, and recreation. Each item is scaled from 1 to 7 and a sum score is calculated to represent higher levels of satisfaction in life (range is 16-112) (Carol S. Burckhardt & Anderson, 2003; C. S. Burckhardt, Woods, Schultz, & Ziebarth, 1989; Offenbächer, Sauer, Kohls, Waltz, & Schoeps, 2012).

Alcohol Intake Screening:

The AUDIT-C is a short, 3-item alcohol screening for hazardous drinkers or active alcohol use disorders. This measure consists of 3 questions to assess an individual's alcohol use. Each question has five possible answers ranging from 0-4 with a total scoring scale of 0-12. A total score of 3 or more in women and a score of four or more in men is suggestive of hazardous drinking or active alcohol use disorders. This form is modified from the longer, 10-item AUDIT instrument (Bradley et al., 2003; Bradley et al., 2007; Bush, Kivlahan, McDonell, Fihn, & Bradley, 1998).

Functional Measures:

Reaction Testing:

Reaction testing will be evaluated by a drop-stick, clinical reaction time apparatus. It is constructed from a meter stick covered in friction tape with gradations. The modified meter stick is fixed to a weighted rubber cylinder. The apparatus is placed between the thumb and index finger of the subject and released at a random time during a countdown. The subject catches the apparatus and the distance fallen (cm) is converted to reaction. Following two practice trials, subjects perform eight trials, and a mean distance value is used for analysis. This is repeated with a second set of 8 trials later during the enrollment visit, and the mean distance value from the second trial will be used as the baseline value. Use of the average distance from the second set of trials will be used as the baseline value so as to avoid the impact of learning effect for this test. This simple clinical measure has been evaluated by Eckner et al, and demonstrated utility in testing comparable to computerized testing methods (Eckner, Kutcher, & Richardson, 2010). Our pilot data demonstrate improved reaction testing associated with use of HIRREM for athletes with persisting post-concussion symptoms (C. H. Tegeler et al., 2016).

Grip Strength:

Grip strength will be evaluated using a hydraulic hand dynamometer (Baseline Hydraulic Hand Dynamometer). The greatest force generated during three trials will be used for analysis (Roberts et al., 2011).

Statistical Analysis:

Continuous variables will be summarized with standard descriptive statistics, such as quartiles, means, and standard deviations, while categorical variables will be summarized with percentages and frequencies. LMMs will be employed to contrast longitudinal changes in systolic and diastolic blood pressure between the HCC and NCC groups. Mean contrasts will be used to compare the changes in blood pressure between groups from V1 to V3, our primary test of efficacy. Comparisons of changes in all secondary outcomes will be assessed in a similar fashion. Assumption and computation diagnostics will be assessed for all model fits (Cheng, Edwards, Maldonado-Molina, Komro, & Muller, 2010), and model adjustments and outcome variable transformations will be made as necessary. Data will be analyzed using SAS v9.4 (SAS Institute, Inc., Cary, NC) or the R Statistical Computing Environment.

Participant Compensation:

Participants will receive up to \$100 compensation for time, travel, and inconvenience related to study visits. Subjects who do not complete the entire study will receive a prorated portion of this amount (\$25 per visit for completion of each of four data collection visits). Participants whose initial BP is too low to meet criteria for pre-hypertension, and are thus considered screen failures, and do not complete the rest of the at the enrollment visit, will still receive a \$10 gift card as compensation for their time.

Human Subjects Protection:

Consent:

Written informed consent will be obtained by the research staff from each competent subject.

Confidentiality and Privacy:

Confidentiality will be protected by collecting only information needed to assess study outcomes, minimizing to the fullest extent possible the collection of any information that could directly identify subjects, and maintaining all study information in a secure manner. Per institutional policy, all research study participants will be assigned a hospital MRN number, if none already exists. To help ensure subject privacy and confidentiality, only a unique study identifier will appear on the data collection form. Any collected patient identifying information corresponding to the unique study identifier will be maintained on a separate master log. The master log will be kept secure, on a separate, limited access user group on a shared network drive, with access limited to designated study personnel. Following data collection subject identifying information will be destroyed at the earliest opportunity, consistent with data validation and study design, producing an anonymous analytical data set. Data access will be limited to study staff. Data and records will be kept locked and secured, with any computer data password protected. No reference to any individual participant will appear in reports, presentations, or publications that may arise from the study.

Brain State Technologies, LLC (BST) may assist with brain pattern analysis. To accomplish this, BST is provided with the first 8 characters from the randomly generated, 36 character identifier that the HIRREM software generates for each participant's brain frequency and amplitude data, along with the participant's age and gender, which are believed important for understanding brain patterns. No other participant-specific information is provided.

Data and Safety Monitoring:

The principal investigator will be responsible for the overall monitoring of the data and safety of study participants. The principal investigator will be assisted by other members of the study staff.

Any collected patient identifying information corresponding to the unique study identifier will be maintained on a separate master log. The master log will be kept secure, with access limited to designated study personnel. Following data collection subject identifying information will be destroyed at the earliest opportunity, consistent with data validation and study design, producing an anonymous analytical data set. Data access will be limited to study staff. Data and records will be kept locked and secured, with any computer data password protected.

Reporting of Unanticipated Problems, Adverse Events, or Deviations:

Any unanticipated problems, serious and unexpected adverse events, deviations or protocol changes will be promptly reported by the principal investigator or designated member of the research team to the IRB and sponsor or appropriate government agency if appropriate.

Appendices

A:

Insomnia Severity Index (ISI)
Center for Epidemiological Studies Depression Scale (CES-D)
Generalized Anxiety Disorder 7-Item (GAD-7)
Epworth Sleepiness Score (ESS)
PTSD Checklist for Civilians (PCL-C)
Perceived Stress Scale (PSS)
Pittsburgh Sleep Quality Index (PSQI)
AUDIT-C
Quality of Life Scale (QOLS)

B:

Handout for Study Participants

C:

Medical History/Screening Form

References:

- Alvarsson, J. J., Wiens, S., & Nilsson, M. E. (2010). Stress recovery during exposure to nature sound and environmental noise. *Int J Environ Res Public Health*, *7*(3), 1036-1046. doi:10.3390/ijerph7031036
- Bastien, C. H., Vallieres, A., & Morin, C. M. (2001). Validation of the Insomnia Severity Index as an outcome measure for insomnia research. *Sleep Med*, *2*(4), 297-307. doi:S1389945700000654 [pii]
- Blanchard, E. B., Jones-Alexander, J., Buckley, T. C., & Forneris, C. A. (1996). Psychometric properties of the PTSD Checklist (PCL). *Behav. Res. Ther*, *34*(8), 669-673. doi:0005-7967(96)00033-2 [pii]

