(Generalized Anxiety Disorder-7, GAD-7), traumatic stress (PTSD Checklist-Civilian, PCL-C), stress (Perceived Stress Scale, PSS), and a quality of life measure (EuroQol Five Dimensions Questionnaire, EQ-5D), as well as drop stick reaction testing, and dynamometry for grip strength. Measures will be collected at an enrollment visit (V1), and the intervention will begin 1-14 days thereafter. BP and heart rate (HR) recording will be repeated prior to the start of the 7th session. Post-intervention data collections will be obtained at 1-7 days (V2), 4-6 weeks (V3, primary outcome), and 12-14 weeks (V4) following completion of the intervention. The primary outcome will be differential change in the systolic and diastolic BP from V1 to V3. Following V4, those in the NCC group will be offered the opportunity to cross over to receive a course of HCC, and will continue to be followed for data collections at 1-7 days (V5), 4-6 weeks (V6), and 12-14 weeks (V7) after completing their crossover HIRREM sessions. We will utilize linear mixed models (LMMs) to contrast longitudinal changes in systolic and diastolic blood pressure between the HCC and NCC groups. Mean contrasts will be used to compare the changes in blood pressures between groups from V1 to V3, our primary test of efficacy. Additional mean contrasts will be constructed to evaluate the consistency of any benefit of HIRREM through subsequent visits beyond V3. Comparisons of changes in all secondary outcomes will be assessed in a similar fashion.

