Importance: This study will explore the use of HIRREM for pre-hypertension, a condition now lacking evidence-based therapies to manage and prevent progression to overt hypertension, in a randomized, controlled clinical trial. The primary outcome of change in blood pressure is a practical, objective physiological parameter. The study will confirm feasibility of a controlled trial using acoustic stimulation interventions in this population, and provide estimates of effect size, which might justify larger controlled trials. A positive result would suggest that HIRREM might have benefit as a noninvasive, non-drug alternative for initial management of pre-hypertension. This, over and above the potential beneficial effects of acoustic stimulation not tied to brain activity, or the impact of interacting with the study personnel and the study environment. The study will also help to identify the characteristics of subgroups that might experience differential effects/benefits from HIRREM. Identification of an effective, noninvasive, non-drug therapy to reduce blood pressure in this cohort could have direct implications for reducing cardiovascular risk in large populations.

Background:

Hypertension, high blood pressure, is the most important risk factor for cardiovascular, and cerebrovascular disease, and thus the leading identifiable cause of death and disability from heart attack and stroke. Combined, these disorders cause > 800,000 deaths annually in the United States, with an estimated direct and indirect cost of over \$316 billion, along with the countless lives impacted. Hypertension affects an estimated 70-80 million people in the USA, but only about half are believed to be adequately treated (Mozaffarian et al., 2016). Hypertension alone costs the nation an estimated \$46 billion annually. Therapy can include an array of changes in life-style, along with medications, but additional, noninvasive, non-drug alternatives are needed.

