In addition to reduction in self-reported symptoms, and improved network connectivity on whole brain, resting MRI studies, all measures HRV and BRS measures increased, showing improved autonomic cardiovascular regulation, with increased parasympathetic influence, and SAP decreased, suggesting improved sympatho-vagal balance (Table 3, below) (Catherine Tegeler, Shaltout, Lee, & Tegeler, 2016; Charles Tegeler, Catherine Tegeler, Jared Cook, Lindsay Howard, et al., 2016; Charles Tegeler, Catherine Tegeler, Jared Cook, Sung Lee, et al., 2016).

Table 3:

Key Autonomic Cardiovascular Outcomes				
Measure (Units)	Mean Value Baseline (SE)	Mean Value Post-HIRREM (SE)	Mean Change (SE)	p value
HF Alpha (ms/mmHg)	17.61 (2.56)	27.28 (3.84)	9.67 (3.09)	p = 0.005
Up SBP (ms/mmHg)	13.06 (1.87)	21.45 (2.99)	8.39 (3.04)	p = 0.011
Down SBP (ms/mmHg)	14.43 (1.78)	22.03 (2.60)	7.61 (2.42)	p = 0.005
Sequence All (ms/mmHg)	13.75 (1.74)	21.41 (2.37)	7.66 (2.20)	p = 0.006
SDNN (ms)	50.98 (5.40)	62.97 (5.23)	11.98 (3.46)	p = 0.003
rMSSD (ms)	32.76 (4.33)	45.98 (5.33)	13.22 (3.00)	p < 0.001
SAP (mmHg)	131.26 (3.18)	125.39 (2.92)	-5.87 (1.91)	p = 0.020

While blood pressure reduction and HRV improvement in these studies could also be secondary to reduced insomnia and anxiety, it may reflect reduced sympathetic tone to blood vessels associated with reduced allostatic load. Additional studies are warranted to investigate the mechanism of the changes associated with this highly promising intervention.

Specific to pre-hypertension, which is the focus for this trial, review of participant data from the ongoing Developmental Study (IRB#00017651) identified 66 participants for whom there was V1 and V2 data, whose baseline BP readings placed them in the category of having pre-hypertension (mean systolic 127.5, diastolic 81.2, and MAP 97.0 mmHg). Participants received a mean of 16.4 HIRREM sessions, over a mean total of 22.4 days, with a mean of 9.5 days actually in the office. Although these participants had only mildly increased BP at baseline (just considered as pre-hypertension), data collection at baseline (V1), and 1-2 weeks after completion of the HIRREM intervention (V2) showed

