statistically significant reductions in systolic arterial pressure (SAP, -4.5 mmHg), diastolic arterial pressure (DAP, -2.7), and mean arterial pressure (MAP, -3.7). There was also significant reduction from V1 to V2 for multiple measures of HRV (SDNN, and rMSSD), and BRS (HF Alpha, and Sequence Up, Sequence Down, and Sequence All). A subset of 28 in this cohort also had a later V3 follow up data collection. For those there was significant reduction in BP, with even larger reductions in BP (SAP, -8.6 mmHg; DAP, -5.2; MAP, -6.3), with still significant improvements in measures of BRS, and a trend for improved HRV (SDNN). These data, as yet unpublished, directly speak to the potential for meaningful reductions in BP associated with HIRREM, in spite of a potential floor effect since baseline BP levels were only in the pre-hypertension category.

Ambient nature sounds are reported to help mitigate stress, and facilitate recovery from stress-related sympathetic hyperarousal. Exposure to nature sound has been shown to facilitate reduce sympathetic activation in response to psychological stress (Annerstedt et al., 2013). While there was significant added benefit to receiving HIRREM, recent preliminary results from our placebo-controlled trial of HIRREM for moderate to severe insomnia also showed significant reduction of symptoms of insomnia for those receiving random acoustic stimulation, not linked to brainwaves (Tegeler CL, 2016). Thus, it is expected that exposure to ambient nature sounds, with accompanying exposure to the study environment, and study personnel, will have some beneficial effects in this setting.

Hypothesis:

The addition of acoustic stimulation linked to brain activity (HIRREM plus continued current care, HCC) will be associated with greater reduction in systolic and diastolic blood pressure than that seen with the addition of acoustic stimulation not linked to brain activity (nature sounds plus continued current care, NCC), among patients with pre-hypertension.

Research Design and Method:

Objectives:

Primary Objective:

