This will be a randomized, single site, controlled, pilot clinical trial. Assuming a potential drop-out rate of 20%, up to 24 subjects will be enrolled to achieve a goal of having at least 20 subjects (10 per group) complete the study, per protocol. Patients who have blood pressures between 120-139 mm/Hg systolic, and/or 80-89 mm/Hg diastolic, as documented by their health care providers on two separate occasions, and no other exclusions, will be randomly assigned to receive either 8-16 sessions of either acoustic stimulation linked to brainwave activity (HCC), or acoustic stimulation not linked to brainwave activity (NCC), over a maximum of 4 weeks, with both groups continuing their current care throughout. There will be pre- and post-intervention data collection to include systolic and diastolic BP, and many secondary outcome measures including measures of autonomic cardiovascular regulation (continuous recording of BP and HR for calculation of measure of HRV and BRS), behavioral symptom outcomes (ISI, PSQI, ESS, CES-D, GAD-7, PCL-C, PSS), quality of life measure (QOLS), alcohol use (Audit C), and function performance measures (drop stick reaction testing, and grip strength). All measures will be collected at an enrollment visit (V1), and the intervention will begin 1-14 days later. BP and HR recordings will also be repeated prior to the start of the 7th session. Post-intervention data collections will be obtained at 1-7 days (V2), 4-6 weeks (V3, primary outcome), and 12-14 weeks (V4) following completion of the intervention. The primary outcome will be differential change in the systolic and diastolic BP from V1 to V3. Additional follow up (V4) will evaluate durability of effects. Following V4, those in the NCC group will be offered the opportunity to cross over to receive a course of HCC, and will continue to be followed for data collections at 1-7 days (V5), 4-6 weeks (V6), and 12-14 weeks (V7) after completing their crossover HCC sessions.

Pre-Hypertension Study Flow Chart

NCC Group Who Complete V1-V4 and Choose to Receive a Course of HCC

Participants/Subjects:

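### Two blood pressures share the primary test: does the plan need a written rule for a result that is significant on only one of them?

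*Combined protocol and SAP*

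**What the plan says.** The Overview under Research Design and Method states: "The primary outcome will be differential change in the systolic and diastolic BP from V1 to V3". The Abstract repeats it. The Hypothesis and the Primary Objective likewise name systolic and diastolic pressure together, joined by 'and'.

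The Statistical Analysis section adds: "Mean contrasts will be used to compare the changes in blood pressure between groups from V1 to V3, our primary test of efficacy". The Abstract has nearly the same sentence and follows it with: "Additional mean contrasts will be constructed to evaluate the consistency of any benefit of HIRREM through subsequent visits beyond V3".

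The Importance paragraph of the Abstract is looser. It says "The primary outcome of change in blood pressure is a practical, objective physiological parameter" and then "A positive result would suggest that HIRREM might have benefit as a noninvasive, non-drug alternative for initial management of pre-hypertension".

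No section gives a significance level, sidedness, an order of testing or a multiplicity method, or says how to describe a result significant on one pressure only. Under Number of Subjects, the plan says that no sample size could be calculated, that up to 24 will be enrolled arbitrarily, and that the aims are feasibility and effect size.

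**The concern.** When a trial has two primary outcomes and one efficacy test, a reader wants to know in advance whether success needs both or either. Requiring both protects the error rate but costs power. Accepting either, each at the full level, raises the chance of a false claim. If nothing is written, the choice can be made after the p-values are seen.

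With about 10 completers per arm a split result is quite possible. Eligibility also allows entry on either pressure, so some participants may have little room to fall on the other. The Importance paragraph speaks of a positive result without defining one, so two analysts could label the same split result differently. At stake would be the headline of the report and the strength of the case for a larger trial.

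**Working it through.** **What the plan lets us reproduce.** It gives no power or error rate. Its only related figure is enrolment: 20 × 1.20 = 24 matches the stated number (20 / 0.80 = 25 is the other convention). This does not bear on a success rule.

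**Inputs from the documents** (all under Specific Relevant Pilot Data, except the arm size)
- Pre-hypertension pilot changes, systolic/diastolic: −4.5/−2.7 mmHg at the pilot's V2 (66 participants) and −8.6/−5.2 mmHg at its V3 (subset of 28). No SDs are given for this cohort.
- SD of change = SE × √n. Table 1 (n = 10): systolic 5.5 × √10 = 17.4, diastolic 3.1 × √10 = 9.8. Table 3 (n = 18): systolic 1.91 × √18 = 8.1. Table 3 lists no diastolic pressure.
- 10 completers per arm, the goal in the Overview.

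**Assumptions not in the documents:** two-sided 5% tests on each pressure; correlation between systolic and diastolic change of 0.5 to 0.8; pilot changes used as between-group differences; diastolic SDs of 5 and 7 as lower values and a systolic SD of 12 as a middle value.

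**Method.** Simulated two-sample t tests on 18 df stand in for the mixed-model contrast. P(exactly one) = P(at least one) − P(both), counting only results that favour HIRREM.

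**Table 1 SDs (17.4/9.8), the only pair that comes from one cohort**

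| Effect (mmHg) | Correlation | Both | At least one | Exactly one |
|---|---|---|---|---|
| −8.6/−5.2 | 0.5 | 7.9% | 30.4% | 22.6% |
| −8.6/−5.2 | 0.8 | 11.7% | 26.2% | 14.5% |
| −4.5/−2.7 | 0.5 | 2.3% | 14.1% | 11.8% |
| −4.5/−2.7 | 0.8 | 4.2% | 12.1% | 7.9% |

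Split results therefore occur in about 8% to 23% of trials.

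**Mixed SDs.** Systolic 8.1 (Table 3) with diastolic 9.8 (Table 1), at −8.6/−5.2, gives exactly one in 42% to 47%. Systolic 17.4 with an assumed diastolic 5 gives the same range. Across the whole grid, exactly one runs from 14% to 47% at −8.6/−5.2 and from 8% to 24% at −4.5/−2.7. No cohort in the documents reports the pairs that produce the top of the range.

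**Smaller effects.** Halving −8.6/−5.2 to −4.3/−2.6, to allow for improvement in the control arm, gives exactly one in 7.5% to 11.4% with Table 1 SDs and 15% to 20% with SDs 8.1/9.8.

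**No true effect**
- 'Either', benefit only: 4.6% at correlation 0.5 and 4.0% at 0.8, against 2.5% for one test.
- 'Both', benefit only: 0.4% and about 1.0%.
- Worst case for 'both' (very large systolic effect, no diastolic effect): 2.5%, the level of a single test.

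**What any rule leaves unchanged.** Both differences and their intervals are the same. The 95% half-width is 2.101 × SD × √(2/10): 7.6 mmHg at SD 8.1, 9.2 at 9.8 and 16.3 at 17.4. In a pilot of this size those widths say more than the label does.

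**The case for a change.** The strongest case for acting is that 'systolic and diastolic' names what is measured and is not a criterion for success. The plan calls the contrast an efficacy test and expects to draw a treatment inference from a positive result, so its pilot status is no full excuse. A clarifying sentence would cost nothing, and split results remain plausible even with halved effects.

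Part of this stands. The rule is not written, and the arithmetic is sound under its assumptions. Three things weaken it.

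- The looser wording is not analysis text. The Importance paragraph uses blood pressure as shorthand. The further contrasts in the Abstract concern persistence across visits. The background sentence "While blood pressure reduction and HRV improvement in these studies could also be secondary to reduced insomnia and anxiety" describes earlier studies with other outcome lists. None of these states an 'either' rule.
- The high percentages rest on weak inputs. The pilot changes are uncontrolled, while the plan expects the nature-sounds arm to improve too. The larger changes come from 28 of 66 participants with a later visit whose timing is not given. The SDs come from other cohorts and from supine continuous recordings, whereas the trial's primary measure is seated and oscillometric.
- The two obvious repairs, requiring both or declaring the pilot estimation-only, are a choice on which statisticians would differ. Neither corrects an error.

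**Conclusion.** No change is needed. This is a missing detail that analysts can fill sensibly: 'systolic and diastolic' runs through the objective, hypothesis and primary outcome, and its natural reading is that both must favour HIRREM. Under that reading the false-benefit rate never exceeds that of one test. A split result would ordinarily be reported as mixed, with both differences shown.

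Even the least favourable reading costs little: false benefit of about 4.0% to 4.6% against 2.5%, assuming two-sided 5% tests and correlation 0.5 to 0.8. A split result might arise in about 8% to 23% of trials with the one same-cohort SD pair, and in up to about 47% with other assumed SDs. These are illustrations, because the plan gives no SD for its target population, no correlation and no significance level. Whatever the frequency, the estimates and intervals do not change. The effect is confined to the wording of a pilot result whose stated purpose is feasibility and effect size.
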